10.6.1. Primary Endpoints

The RR is defined as the percentage of responders (CR+PR) among those patients who are evaluable for response. Response rate will be presented as the point estimate along with 95% confidence intervals calculated using both asymptotic normal approximation and exact binomial methods.

The DCR is defined as the percentage of patients who do not exhibit progression (CR+PR+SD) among those patients who are evaluable for response at 6 months. Disease control rate will be presented as the point estimate along with 95% confidence intervals calculated using both asymptotic normal approximation and exact binomial methods.

CONFIDENTIAL

STUDY DRUG: Orteronel

SCRI INNOVATIONS STUDY NUMBER: BRE 203

DATE OF PROTOCOL: Version 3.0 30 October 2013

Page 55 of 80

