Correlative Testing:	
The following correlative testing will included:
 
 • Measurement of changes in serum estradiol levels, total and free testosterone levels, and SHBG • Measurement of changes in ACTH, DHEA-S, and cortisol levels • Biomarker testing of archived tumor tissue for loss of PTEN and PIK3CA mutations.

CONFIDENTIAL

STUDY DRUG: Orteronel

SCRI INNOVATIONS STUDY NUMBER: BRE 203

DATE OF PROTOCOL: Version 3.0 30 October 2013

BRE 203 CLINICAL PROTOCOL SYNOPSIS

Statistical Methodology:	
For patients with ER-/PR-/HER2-/AR+ tumors (Cohort 1), the expected response rate with standard anti-estrogen therapy is expected to be zero. Therefore, a response rate of at least 10% with orteronel therapy would indicate activity and would lead to further investigation. Assuming an evaluable population of 28 patients, the exact 95% confidence intervals (CIs) for a hypothesized response rate of 11% is (2.4%, 28.6%). In order to incorporate an early stopping rule, Simon's two-stage design is applied using alpha = 0.10 and power = 0.80 with comparison of the hypothesized response rate of 11% versus a conservative value of 2%. Initially, 19 patients will be enrolled in this cohort, and if no responses are observed, recruitment to this cohort will stop. Otherwise, enrollment in this cohort will continue to full accrual of 28 patients. To account for an unevaluable rate of 10%, a total of 31 patients will be enrolled in this cohort.
 
For patients with ER+ and/or PR+/AR+ tumors (Cohort 2), published data on exemestane as third-line hormonal therapy in postmenopausal women indicate a response rate of 13% and a clinical benefit rate (CR, PR, or SD >24weeks) of 30%. It is hypothesized that treatment with orteronel in this patient population will produce similar results. Assuming an evaluable population of 50 patients, the exact 95% CIs for a hypothesized response rate of 14% is (5.8%, 26.7%). In order to incorporate an early stopping rule, Simon's two-stage design is applied using alpha = 0.10 and power = 0.80 with comparison of the hypothesized response rate of 14% versus a conservative value of 5.1%. Initially, 26 patients will be enrolled in this cohort, and if one or no responses are observed, recruitment into this cohort will stop. Otherwise, enrollment in this cohort will continue to full accrual of 50 patients. To account for an unevaluable rate of 10%, a total of 55 patients will be enrolled in this cohort.

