10.3. Sample Size Considerations

Up to 86 patients will be enrolled into this study.

Sample size computations are as follows for each patient cohort.

Cohort 1: For patients with ER-/PR-/HER2-/AR+ tumors, the expected response rate with standard anti-estrogen therapy is expected to be zero. Therefore, a response rate of at least 10% with orteronel therapy would indicate activity and would lead to further investigation. Assuming an evaluable population of 28 patients, the exact 95% confidence interval (CI) for a hypothesized response rate of 11% is (2.4%, 28.6%). In order to incorporate an early stopping rule, Simon's two-stage design is applied using $\alpha = 0.10$ and $\text{power} = 0.80$ with comparison of the hypothesized response rate of 11% versus a conservative estimate of 2%. Initially, 19 patients will be enrolled in this cohort, and if no responses are observed, recruitment to this cohort will stop. Otherwise, enrollment in Cohort 1 will continue to full accrual of 28 evaluable patients. To account for an unevaluable rate of 10%, a total of 31 patients will be enrolled in this cohort.

Cohort 2: For patients with ER+ and/or PR+/AR+ tumors, published data on exemestane as third-line hormonal therapy in postmenopausal women indicate a response rate of 13% and a clinical benefit rate (CR, PR, or SD >24 weeks) of 30%. It is hypothesized that treatment with orteronel in this patient population will produce similar results. Assuming an evaluable population of 50 patients, the exact 95% CI for a hypothesized response rate of 14% is (5.8%, 26.7%). In order to incorporate an early stopping rule, Simon's two-stage design is applied using $\alpha = 0.10$ and $\text{power} = 0.80$ with comparison of the hypothesized response rate of 14% versus a conservative estimate of 5.1%. Initially, 26 patients will be enrolled in this cohort, and if one or no responses are observed, recruitment into this cohort will stop. Otherwise, enrollment in

CONFIDENTIAL

STUDY DRUG: Orteronel

SCRI INNOVATIONS STUDY NUMBER: BRE 203

DATE OF PROTOCOL: Version 3.0 30 October 2013

Cohort 2 will continue to full accrual of 50 evaluable patients. To account for an unevaluable rate of 10%, a total of 55 patients will be enrolled in this cohort.

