10.4. Planned Interim Analyses

Based on Simon's two-stage design, each cohort individually will undergo an interim analysis for efficacy.

Cohort 1: After enrollment of the first 19 evaluable patients and if no responses are observed, recruitment to this cohort will stop due to lack of efficacy. Otherwise, enrollment will continue to full accrual of 28 evaluable patients. If two or more patients exhibit response at the final analysis, the trial will be considered successful with respect to this patient population.

Cohort 2: After enrollment of the first 26 evaluable patients and if one or no responses are observed, recruitment to this cohort will stop due to lack of efficacy. Otherwise, enrollment will continue to full accrual of 50 evaluable patients. If five or more patients exhibit response at the final analysis, the trial will be considered successful with respect to this patient population.

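### The response-rate interval is single-stage and at 95%, so it is not exact for the Simon design and covers the null at the lowest success counts

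*Combined protocol and SAP*

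**What the plan says.** The synopsis states that "Simon's two-stage design is applied using alpha = 0.10 and power = 0.80". Section 10.3 gives the hypotheses: for Cohort 1, "comparison of the hypothesized response rate of 11% versus a conservative estimate of 2" (percent), and for Cohort 2, "comparison of the hypothesized response rate of 14% versus a conservative estimate of 5.1" (percent).

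Section 10.4 gives the rules. The interim rule of the first cohort reads: "After enrollment of the first 19 evaluable patients and if no responses are observed, recruitment to this cohort will stop due to lack of efficacy". With at least one response, that cohort goes on to a total of 28 evaluable patients, and a final count of at least two responses is a success. Cohort 2 stops on zero or one response in 26 evaluable patients and otherwise continues to 50. Its success rule reads: "If five or more patients exhibit response at the final analysis, the trial will be considered successful with respect to this patient population".

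Section 10.6.1 then sets the reporting: "Response rate will be presented as the point estimate along with 95% confidence intervals", calculated by the asymptotic normal and the exact binomial method. No section names an interval that allows for the interim stop, or one at the level of the test. No section makes the interval a criterion for success.

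**The concern.** An exact binomial interval assumes a fixed number of patients. Here the number depends on the first-stage result, so the usual formula does not invert the distribution the data come from, and its stated coverage is no longer guaranteed.

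Separately, a two-sided 95% interval leaves 2.5% in each tail, while the design tests at 10% in one tail. A cohort can therefore meet its success count while the interval printed beside it includes the null rate. The reader then has two statements about the same null at different levels and no sentence saying which one governs. At stake is the reading of a marginal positive result. The go/no-go rule itself is not at stake.

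**Working it through.** **Inputs (Sections 10.3 and 10.4).** Cohort 1: first stage 19, stop at 0, total 28, success at 2 or more, null 2%, alternative 11%. Cohort 2: first stage 26, stop at 0 or 1, total 50, success at 5 or more, null 5.1%, alternative 14%. Alpha 0.10 is taken as one-sided, as is usual for Simon's design; the documents do not state the sidedness.

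**1. Reproduce the design.** The probability of success is P(continue and total ≥ threshold). For Cohort 1 this is 1 − (1−p)^19 − 19p(1−p)^27.
- At p = 0.02: 1 − 0.6812 − 0.2202 = 0.0985. At p = 0.11: 0.801.
- Cohort 2, by the same enumeration: 0.0973 at 5.1% and 0.806 at 14%.

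Both designs meet alpha 0.10 and power 0.80. The illustrative exact intervals in Section 10.3 also reproduce: (2.40%, 28.59%) for 11% of 28 (3.08 responses) and (5.82%, 26.74%) for 7/50.

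**2. Does the single-stage exact 95% interval keep 2.5% above its upper limit?** Add the probabilities of all outcomes whose upper limit lies below the true rate.
- Cohort 1, true rate 18.35%, just above the upper limits of 0/19 (17.65%) and 1/28 (18.348%): (0.8165)^19 + 19(0.1835)(0.8165)^27 = 0.0212 + 0.0146 = 0.0359. Coverage at this rate is 94.2%.
- Cohort 2, true rate 19.65%, just above the upper limits of 1/26 (19.64%) and 4/50 (19.23%): P(0 or 1 in 26) + P(continue, total 2 to 4) = 0.0034 + 0.0215 + 0.0137 = 0.0386.

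The miss below the lower limit stays within 2.5% in both cohorts.

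**3. Intervals at the success counts.** Two-stage limits solve P(continue and total ≥ s) = a for the lower limit and P(stop, or total ≤ s) = a for the upper limit, with a = 0.025 or 0.10.

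| Result | Null | Single-stage 95% | Single-stage 80% | Two-stage 95% | Two-stage 80% |
|---|---|---|---|---|---|
| 2/28 | 2% | 0.88–23.5 | 1.92–17.9 | 0.92–23.8 | 2.02–18.1 |
| 3/28 | 2% | 2.27–28.2 | 4.00–22.3 | 2.29–28.3 | 4.04–22.4 |
| 5/50 | 5.1% | 3.33–21.8 | 4.94–17.8 | 3.45–22.7 | 5.14–18.3 |
| 6/50 | 5.1% | 4.53–24.3 | 6.43–20.1 | 4.61–24.7 | 6.54–20.4 |
| 7/50 | 5.1% | 5.82–26.7 | 7.96–22.4 | 5.86–26.9 | 8.02–22.5 |

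At 95%, allowing for the stop moves the lower limit only from 0.88% to 0.92% and from 3.33% to 3.45%. The level is therefore the main cause of the overlap with the null. At the threshold counts both changes are needed: the single-stage 80% limits (1.92%, 4.94%) and the two-stage 95% limits still cover the null. The two-stage 80% lower limit inverts the same tail probability that defines success, so it agrees with the rule by construction.

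**4. How often this occurs among successes, if the alternative is true.** Cohort 1: P(2/28) / P(success) = 0.200 / 0.801 = 25%. Cohort 2: P(5 or 6 of 50) / P(success) = 0.254 / 0.806 = 32%. The normal-approximation interval, also planned, covers the null at 2 to 4 of 28 and 5 to 7 of 50.

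**5. Point estimate.** Bias is the expected plain proportion over all outcomes, minus p. In Cohort 1 a stopped cohort contributes 0, so at p = 0.02 the expectation is (19×0.02 + 9×0.02×0.3188)/28 = 0.0156, a bias of −0.44 points. At 11% it is −0.39. In Cohort 2 it is −0.84 at 5.1%, −0.96 at 8% and −0.54 at 14%.

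**The case against.** The strongest reply is that nothing in the plan contradicts itself. Section 10.4 judges success by a count, and Section 10.6.1 only presents an interval. A 95% interval beside a test at 0.10 is ordinary reporting, and it will sometimes cover the null near the threshold. The intervals that Section 10.3 itself shows at the hypothesized rates exclude both nulls. This stands, and it limits the point to reporting.

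A reader might infer three stronger things that the documents do not support.
- *Any successful cohort will carry an interval that covers its null.* With the exact method this happens only at 2/28 and at 5 or 6 of 50, a minority of successes at the design alternatives.
- *Ignoring the stopping rule causes the overlap.* It contributes little at 95%; the confidence level does most of it.
- *The plain rate is misleading and must be replaced.* Its overall bias is downward, which is conservative for a claim of activity, and under 1 point. Among cohorts declared successful at the null rate, the plain rate already averages 7.9% (true 2%) and 11.1% (true 5.1%). The uniformly minimum variance unbiased estimate (UMVUE) is higher still, at 8.5% and 12.1%.

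The agreement at 80% is also narrow: the lower limits clear the nulls by 0.02 and 0.04 points, and only at exactly 28 and 50 evaluable patients. With 29 evaluable in Cohort 1, P(2 or more responses and continue) at 2% is 1 − 0.98^19 − 19(0.02)(0.98)^28 = 0.103, and the 80% interval covers the null again. The plan enrolls 31 and 55, so the evaluable number may differ. This too stands. It is a reason to compute the interval from the numbers actually attained and to say that the count governs. It does not justify keeping a single-stage formula.

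**Conclusion.** The point holds as a minor reporting defect. The planned exact interval is not exact for the design: its upper-tail miss reaches about 3.6% and 3.9% where 2.5% is nominal. At 2/28, 5/50 and 6/50 it covers the null that the design has just rejected at one-sided 0.10. From 3/28 and 7/50 the exact interval excludes the null.

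The success rule, its alpha (0.0985 and 0.0973) and its power (0.801 and 0.806) are not affected. The conclusion assumes a one-sided alpha, exactly 28 and 50 evaluable patients, and interim looks at exactly 19 and 26.

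**What to change.** In Section 10.6.1:
- Replace the single-stage exact interval for the response rate with an exact interval from the two-stage sampling distribution, using stagewise ordering and the evaluable numbers attained.
- Give it at the two-sided 80% level, which matches one-sided alpha 0.10, alongside the 95% level.
- State that success is judged by the response count in Section 10.4, and that the 95% interval describes precision and may cover the null at the lowest success counts.
- Keep the plain proportion as the point estimate. The UMVUE may be shown as a sensitivity figure (7.9% against 7.1% at 2/28; 11.2% against 10.0% at 5/50).

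The cost is a few lines of code, one more interval in the table and slightly wider upper limits at 95% (23.8% against 23.5% at 2/28; 22.7% against 21.8% at 5/50). No sample size, threshold or patient procedure changes.

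### Section 10.6.1 plans a normal-approximation 95% CI beside the exact one without saying which governs, and for response rate the normal interval fails at the low counts this design expects

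*Combined protocol and SAP*

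**What the plan says.** Section 10.6 makes RR and DCR the primary efficacy endpoints in both cohorts. Section 10.6.1 defines RR as the "percentage of responders (CR+PR) among those patients who are evaluable for response". For the RR result it then asks for two 95% intervals side by side, "calculated using both asymptotic normal approximation and exact binomial methods". DCR gets the same treatment. Nothing in Section 10 ranks the two intervals.

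The other parts of the plan that bear on this are:

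- **Section 10.3** quotes only exact intervals: 2.4% to 28.6% for 11% in 28 evaluable patients (Cohort 1), and 5.8% to 26.7% for 14% in 50 (Cohort 2). The design rates are 2% against 11% in Cohort 1 and 5.1% against 14% in Cohort 2.
- **Section 10.4** bases decisions on counts. The stopping rule for the triple-negative cohort reads: "After enrollment of the first 19 evaluable patients and if no responses are observed, recruitment to this cohort will stop due to lack of efficacy". Success there is declared "If two or more patients exhibit response at the final analysis". Cohort 2 stops at one or no responses in 26 and succeeds at five or more in 50.

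**The concern.** The normal approximation to a binomial proportion breaks down when the number of responders is small, and this design expects few. The likely results include 0/19, 1/26 and 2 or 3 of 28. At such counts the normal interval can run below zero or shrink to a point, and it is narrower than the exact interval, so it overstates precision.

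With no order of precedence, the report would carry two different 95% intervals for the same primary result, and either could later be quoted as the confidence interval. For a cohort that stops or fails, the normal interval can appear to rule out the target response rate when the data do not.

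**Working it through.** **Inputs.** Section 10.3: rates 2% and 11% (Cohort 1), 5.1% and 14% (Cohort 2). Section 10.4: stop at 0/19, otherwise continue to 28; stop at 0 or 1 of 26, otherwise continue to 50. Section 10.6.1: two-sided 95% intervals among evaluable patients. The 5% rate in step 4 is an added intermediate value, not a design rate.

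**Step 1: reproduce the plan's figures.** The exact (Clopper-Pearson) interval for 7/50 is 5.8% to 26.7%, as stated. The Cohort 1 interval of 2.4% to 28.6% is matched with 0.11 × 28 = 3.08 responders; the whole-number result 3/28 gives 2.3% to 28.2%. Exact two-stage sums give alpha 0.0985 and power 0.801 (Cohort 1), and 0.0973 and 0.806 (Cohort 2), in line with the stated 0.10 and 0.80.

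**Step 2: the intervals.** The normal interval is p̂ ± 1.96 × √(p̂(1 − p̂)/n). For 2/28: 0.0714 ± 1.96 × √(0.0714 × 0.9286/28) = 0.0714 ± 0.0954, that is −2.4% to 16.7%. The exact upper limit at 0/19 is 1 − 0.025^(1/19) = 17.6%.

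| Result | Role in the design | Normal 95% | Exact 95% |
|---|---|---|---|
| 0/19 | Cohort 1 stop | 0 to 0 | 0 to 17.6 |
| 1/28 | Cohort 1 final failure | −3.3 to 10.4 | 0.1 to 18.3 |
| 2/28 | Cohort 1 success threshold | −2.4 to 16.7 | 0.9 to 23.5 |
| 3/28 | about 11% | −0.7 to 22.2 | 2.3 to 28.2 |
| 1/26 | Cohort 2 stop | −3.5 to 11.2 | 0.1 to 19.6 |
| 5/50 | Cohort 2 success threshold | 1.7 to 18.3 | 3.3 to 21.8 |
| 7/50 | 14% | 4.4 to 23.6 | 5.8 to 26.7 |

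The normal lower limit is negative when x < 3.84n/(n + 3.84). That bound is 3.2, 3.4, 3.4 and 3.6 for n = 19, 26, 28 and 50. So it is negative at 1 to 3 responses and positive from 4 on.

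**Step 3: where the two intervals disagree.**

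- At 0/19 and 1/28 the normal interval excludes the hypothesized 11%; the exact interval includes it.
- At 1/26 the normal interval excludes 14%; the exact interval includes it.
- At 3/28 the exact interval excludes the 2% null; the normal interval includes it.
- At 7/50 the exact interval excludes 5.1%; the normal interval includes it.

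**Step 4: coverage.** For each true rate, list every possible final result under the stopping rule and add the probabilities of those whose interval contains the true rate.

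| Cohort, true rate | Normal | Exact | Main sources of the normal interval's non-coverage |
|---|---|---|---|
| 1, 2% | 32% | 98.2% | 0/19: 68.1 points (0.98^19 = 0.681) |
| 1, 5% | 62% | 98.8% | 0/19: 37.7 points |
| 1, 11% | 79% | 99.1% | 0/19: 10.9; 1/28: 9.0 |
| 2, 5.1% | 74% | 98.7% | 0/26: 25.6 |
| 2, 14% | 86% | 95.8% | 1/26: 8.4; 3/50: 2.4; 0/26: 2.0 |

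**Step 5: where the normal interval does tolerably.** With a fixed 50 patients its coverage is 92.3% at 5.1% and 92.6% at 14%. For DCR, the only related figure in the documents is the 30% clinical benefit rate in Section 10.3. At 30%, fixed-n coverage is 93.2% (n = 28) and 93.5% (n = 50), and 15/50 gives 17.3% to 42.7% against an exact 17.9% to 44.6%.

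**The case against.** The strongest reply is that a valid interval is already planned and no decision uses the other one. Both statements are correct. A reader might infer that the trial lacks a sound confidence interval, or that its go/no-go conclusions are at risk. The documents support neither: the exact interval is in the same sentence of Section 10.6.1, and Section 10.4 decides on response counts alone. No alpha, power or sample size changes.

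A second reply is that the very low coverage reflects cohorts stopped with no responses, where few readers would take an interval of 0 to 0 at face value beside 0 to 17.6%. This explains almost all the loss at 2%, 5% and 5.1%. It explains about half of it at 11% (10.9 of 20.8 points) and little at 14%, where the larger part is the 1/26 stop. Results such as 1/26 and 1/28 give normal intervals that look ordinary once a negative limit is cut off at zero, yet exclude the target rate.

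A third reply concerns scope, and it stands. A reader might infer that the normal interval fails for every rate from 2% to 14% and every size from 19 to 50. It does not: its limits are positive from 4 responses on, 0/28, 0/50 and 1/50 cannot occur under the stopping rules, and coverage at a fixed 50 patients is close to nominal at the design rates. Nor do the figures show an error for DCR near 30%.

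**Conclusion.** The point holds for RR, as a matter of reporting. Followed as written, Section 10.6.1 would put beside the primary RR result a second 95% interval whose true coverage under the planned stopping rules is 32% to 79% at the Cohort 1 design rates and 74% to 86% at those of Cohort 2, against 95.8% to 99.1% for the exact interval. It would also leave open which of the two is the trial's confidence interval. For DCR near 30% the normal interval is redundant rather than wrong.

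Assumptions: the normal interval is the standard Wald form; a continuity correction does not rescue it, since 0/19 becomes −2.6% to 2.6%. Evaluable numbers are exactly 19 or 28 and 26 or 50. The plan states no expected DCR for either cohort, so the DCR conclusion applies only near the borrowed 30%. Neither interval adjusts for the two-stage stopping, but the unadjusted exact interval still covers at least 95.8% at the design rates.

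**What to change.** In Section 10.6.1, delete the normal-approximation interval for RR and name the exact binomial (Clopper-Pearson) interval as the reported 95% CI. This matches Section 10.3, which already uses only exact intervals. Apply the same wording to DCR so that both primary endpoints are reported alike. If a second, less conservative interval is wanted, the Wilson score interval avoids the worst behaviour (0/19: 0 to 16.8%; 2/28: 2.0% to 22.6%), but it should be labelled supplementary.

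The cost is one sentence in the plan and one fewer line in the output. Sample size, data collection, stopping rules and success criteria are unchanged.

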10.6.2. Secondary Endpoints

Progression-free survival (PFS) and OS will be analyzed using Kaplan-Meier methods. Each of these endpoints will be presented graphically and further reported using the respective median time point estimate along with its 95% CI.

PFS will be measured from the date of first protocol treatment until the date of objective disease progression or date of death is documented (event), or date of last adequate tumor assessment (censored). If a patient receives non-protocol therapy for the study indication prior to incurring an event, the earliest date of non-protocol treatment recorded will be used (censored). If no post-treatment tumor assessment has been performed, PFS for the patient will be censored at time zero.

OS will be measured from the date of first protocol treatment until the date of death is documented (event), or date last known alive (censored). If a patient receives non-protocol therapy for the study indication prior to incurring an event, the earliest date of non-protocol treatment recorded will be used (censored).

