7.5. End of Study Treatment

Patients are permitted to continue treatment with orteronel until disease progression, or the patient is discontinued due to unacceptable toxicity or a decision to discontinue treatment by the patient or the study physician. Patients will return to the study center \leq 30 days after treatment ends for the following assessments:

- Update of medical history
- Physical examination including measurement of weight and vital signs
- ECOG performance status
- AE assessment
- Concomitant medication review
- Study drug compliance assessment
- CBC, including 3-part differential and platelets
- CMP
- Fasting plasma glucose, insulin, c-peptide, and HbA_{1c} (only in patients with a history of diabetes)
- Serum hormone levels: estradiol, total and free testosterone, SHBG, ACTH, DHEA-S, and cortisol

CONFIDENTIAL

STUDY DRUG: Orteronel

SCRI INNOVATIONS STUDY NUMBER: BRE 203

DATE OF PROTOCOL: Version 3.0 30 October 2013

- Serum amylase/lipase
- Urinalysis
- CT scan of the chest /abdomen/pelvis, if no documented progressive disease and the last assessment was >8 weeks prior (only those scans abnormal at baseline need to be repeated)

If treatment is discontinued because of toxicity or any other reason(s) at a treatment visit and no study treatment is administered, that visit may fulfill the End-of-Treatment Visit.

After withdrawal from protocol treatment, patients must be followed for AEs for 30 calendar days after the last dose of study drug.

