7.6. Follow-Up

7.6.1. Follow-Up After Discontinuing Study Treatment

Patients discontinuing treatment for any reason other than progressive disease will be monitored for evidence of disease progression. Disease progression will be assessed every 6 months for 2 years and annually thereafter, up to a maximum of 5 years after the last patient has enrolled on the study. Imaging scans will be done as clinically indicated for evaluation of any new symptoms and assessment for disease progression. After disease progression is documented, patients will be followed as specified in Section 7.6.2.

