11.4.9. Lack of Efficacy

When there is deterioration in the condition for which the study treatment is being used, there may be uncertainty as to whether this is lack of efficacy or an AE. In such cases, unless the Sponsor or reporting physician considers the study treatment contributed to the deterioration of the condition, the deterioration should be considered lack of efficacy and not an AE.

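### PFS counts only objective progression or death, so a patient stopped for worsening disease without RECIST progression is informatively censored and the Kaplan-Meier PFS is biased upward

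*Combined protocol and SAP*

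**What the plan says.** **Event and censoring (10.6.2).** "Progression-free survival (PFS) and OS will be analyzed using Kaplan-Meier methods", with a median and 95% CI. The event rule is "until the date of objective disease progression or date of death is documented (event". Without an event, the patient is censored by one of three rules:

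- the default, "or date of last adequate tumor assessment (censored";
- if other therapy for the disease starts first, "the earliest date of non-protocol treatment recorded will be used (censored";
- for a patient never scanned after starting the drug, "If no post-treatment tumor assessment has been performed, PFS for the patient will be censored at time zero".

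**Stopping treatment (3.3, 7.5).** Disease progression is a reason to stop in both sections, without the qualifier objective. Section 7.5 also lets the patient or the study physician decide to stop.

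**Imaging around the stop (7.4.2, 7.5).** CT is 8-weekly from Cycle 3 Day 1. The end-of-treatment CT is needed only "if no documented progressive disease and the last assessment was >8 weeks prior". That visit may fall up to 30 days after treatment ends.

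**After the stop (7.6.1, 7.6.2).** "Patients discontinuing treatment for any reason other than progressive disease will be monitored for evidence of disease progression". This follow-up is 6-monthly for 2 years and then annual, with imaging only when clinically indicated. Once progression is documented, only survival is followed.

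**Definition of progression (9.1, 9.2.2).** Progression is judged by RECIST 1.1. No clinical or symptomatic category is defined.

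Sections 10.5 and 10.6 plan no sensitivity analysis for PFS.

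**The concern.** A patient who worsens between scans and is taken off treatment before RECIST progression is shown has failed treatment, but has no PFS event on that date. Every route that Section 10.6.2 then offers either removes the patient from the risk set without an event or dates the event later. Kaplan-Meier assumes that censored patients have the same prospects as those still followed, and these patients do not. Time-zero censoring is the extreme case, because an early failure then contributes nothing to the curve.

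The situation is plausible here. Patients with bone-only metastases are eligible (3.1, criterion 2), while bone scans are done only if clinically indicated (7.4.2).

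PFS is a named secondary efficacy endpoint of a single-arm trial in refractory disease. No control arm shares the bias, so the median would be read at face value.

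**Working it through.** **The plan's own figure.** There is none to reproduce: no PFS median, event target or power is stated. The interim and final rules in Section 10.4 use response counts only.

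**Inputs.** From the documents: 8-weekly scans, and 31 and 55 patients. Assumed: exponential progression times with median *m* = 14 weeks (Cohort 1) or 20 weeks (Cohort 2), and a share *q* = 10% to 30% of progressions that are clinical only.

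**Step 1: probability of progressing in one scan interval.** p = 1 − 2^(−8/m), which is 0.327 for m = 14 and 0.242 for m = 20.

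**Step 2: clinical progression counted as an event.** S(24) = (1 − p)^3 = 2^(−24/m), which is 30.5% and 43.5%.

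**Step 3: censored at the last scan, or at time zero before the first.** Clinical progressors leave before the next scan. Of those who start an interval, 1 − pq are at risk at the next scan and p(1 − q) are events. The survival factor per interval is (1 − p)/(1 − pq), so S(24) = [(1 − p)/(1 − pq)]^3.

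| | q = 10% | 15% | 20% | 30% |
|---|---|---|---|---|
| m = 14 (event rule 30.5%) | 33.7% | 35.4% | 37.3% | 41.5% |
| m = 20 (event rule 43.5%) | 46.8% | 48.6% | 50.5% | 54.6% |
| Excess, points (both) | about 3 | about 5 | about 7 | about 11 |

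The standard error of 24-week PFS is about √(0.305 × 0.695/31) = 8.3 points in Cohort 1 and √(0.435 × 0.565/55) = 6.7 points in Cohort 2. The excess is therefore about 0.4 to 1.6 standard errors.

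**Step 4: median.** It moves only when the curve crosses 50% at a different scan.

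- Cohort 1, week 16, [(1 − p)/(1 − pq)]^2: 0.453 under the event rule; 0.484, 0.501, 0.518 and 0.557 for the four shares. The median stays at 16 weeks at 10%, is on the boundary at 15%, and is 24 weeks from 20%.
- Cohort 2, week 24 (table): the median stays at 24 weeks up to 15% and is 32 weeks from 20%.

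**Step 5: time zero.** The share is pq. Cohort 1: 31 × 0.327 × 0.10 to 0.30 = 1.0 to 3.0 patients. Cohort 2: 55 × 0.242 × 0.10 to 0.30 = 1.3 to 4.0 patients.

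**Step 6: adding the CT rule of Section 7.5.** Further assumptions: baseline scan uniform over the 4 weeks before treatment (the window in 7.3), end-of-treatment visit uniform over 0 to 30 days after the stop, and the CT shows progression. By simulation, about 30% of clinical stops then get a CT. The excess falls to about 3 to 8 points and time-zero censoring roughly halves, to about 0.5 to 2 patients per cohort. At a 20% share the medians are about 17 and 24 weeks, so the shift largely disappears; at 30% it remains (24 and 32 weeks). If every visit falls on the stop day, only about 6% get a CT and the excess is close to that in Step 3.

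**Step 7: the other routes in 10.6.2.** Simulated 24-week PFS with 20,000 patients, m = 16 weeks and q = 20%:

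| Handling of clinical-only progression | 24-week PFS |
|---|---|
| Event on its date | 35.4% |
| Censored at last scan or time zero | 42.5% |
| Censored at new therapy (assumed 3 weeks later) | 43.1–43.4% |
| Event only at later death (assumed median 26 weeks later) | 44.6% |

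The direction is upward on every route. Over medians of 8 to 24 weeks, the last-scan rule gives about 2 to 11 points.

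**The case against.** The strongest answer is that Section 9.1 ties progression to RECIST 1.1. Read that way, progressive disease in Section 7.6.1 already means RECIST progression. A patient stopped without it falls under the physician's or patient's decision in Section 7.5 and stays under progression follow-up. This stands in part. A reader might infer that the plan ends tumour follow-up for clinical progressors, but no passage says so. What remains is that sites may code the same stop differently, that imaging after the stop is only as indicated, and that new therapy censors before any later scan can count. The upward bias survives this reading.

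Four stronger inferences are not supported:

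- **Always censored at the last scan.** New therapy and death each have their own rule, and survival is still followed.
- **Always time zero before week 8.** The baseline scan may be 4 weeks old at the start of treatment, so a stop from about week 4 can already trigger the end-of-treatment CT. Section 10.6.2 also does not say that time zero overrides a death before the first scan.
- **Section 11.4.9 supports the point.** It settles only whether deterioration is recorded as an adverse event.
- **Later deaths reduce the bias.** In the comparison above, the death-only route gives a higher 24-week PFS than the last-scan rule (44.6% against 42.5%).

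It is also fair to say that the size rests on assumed inputs, that the jump in the median partly reflects the 8-week scan grid, and that PFS is descriptive.

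**Conclusion.** The point holds as a bias in a secondary endpoint. A patient stopped for worsening disease without RECIST progression is not an event at that date, the censoring is informative, and Kaplan-Meier PFS is too high. With assumed medians of 14 to 20 weeks and 10% to 30% of progressions clinical only, 24-week PFS rises by about 3 to 11 points, or about 3 to 8 with the Section 7.5 CT rule and visits spread over 30 days. The median is unchanged or moves by up to one 8-week interval. The direction does not depend on which Section 10.6.2 route applies, but the size does depend on the assumptions.

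A reader might infer that the trial's go/no-go decision is at risk. It is not, because the two-stage rules use response counts and neither primary endpoint uses the PFS censoring rules. This is a cheap improvement that should be made, not a flaw that undermines the design.

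**What to change.** Keep objective PFS as the main analysis.

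1. In Section 10.6.2, pre-specify one supportive PFS analysis in which a stop for disease progression without RECIST progression is an event on the stop date. Such patients are not censored at time zero in that analysis.
2. In Section 10.6.2, state that death before the first scan is an event and is not overridden by the time-zero rule.
3. Report the number of patients stopped for progression without RECIST progression, by cohort.
4. In Section 7.6.1, clarify progressive disease as RECIST 1.1 progressive disease, so that patients stopped without it remain under progression follow-up.

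The cost is one extra Kaplan-Meier run per cohort and a few wording changes, with no new procedure. The downside is that clinical progression is less objective than RECIST, so this analysis is supportive only and is shown beside the main curve.
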